12.1.6 Benefit-risk Assessment

See Section 2.2 of the core protocol for an overall benefit-risk assessment for AZD0466 in the study population.

Module 2 will utilise a dose of AZD0466 that has been declared tolerable in patients with AML or ALL during the dose escalation Part A of Module 1. With the exception of abnormal LFTs, the most common adverse reactions during treatment with voriconazole do not overlap with the potential risks of treatment with AZD0466. The study protocol incorporates mandatory safety monitoring procedures, including intensive more frequent assessments of

liver biochemistry than for other clinical chemistry parameters, dose modification guidelines, and additional guidance for management of specific AEs.

The available nonclinical and clinical information supports an acceptable benefit-risk assessment for investigation of potential DDI between AZD0466 and voriconazole in patients with advanced haematological malignancies for which there are limited treatment options.

12.2 OBJECTIVES AND ENDPOINTS - MODULE 2

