11.6.2.9.4 Clinical Chemistry

Blood samples for determination of clinical chemistry will be collected as specified in [Table 16](#) and [Table 17](#). Unscheduled samples may be collected if deemed clinically warranted, and results of unscheduled assessment should be recorded in the eCRF.

If an unscheduled ECG is performed for patient assessment, an electrolyte panel (ie, calcium, magnesium potassium) must be done. If clinically indicated, a troponin assay should coincide with this evaluation. Cardiac troponin I is preferred when available, however if not, cardiac troponin T is acceptable. To allow comparison with baseline, sites are requested to maintain consistency with the troponin assay used. Isolated troponin elevations are not sufficient to trigger dosing changes and should be evaluated in the context of other cardiac findings.

The following clinical chemistry tests will be performed ([Table 19](#)):

Table 19 Clinical Chemistry

Albumin	Cholesterol ^a	Magnesium
Alkaline phosphatase	C-reactive protein	Phosphate
Alanine aminotransferase	Creatinine	Potassium
Amylase ^b	Gamma-glutamyl transferase	Sodium
Aspartate aminotransferase	Glucose ^a	Triglycerides ^a
Bicarbonate	Glutamate dehydrogenase ^b	Total protein
Bilirubin (total and direct)	Lactate dehydrogenase	Chloride
Blood urea nitrogen	Lipase ^c	Uric acid
Calcium		

^a Fasting cholesterol, triglyceride and glucose values are not required. However, if non-fasting values are abnormal, a repeat sample should be obtained when the patient is fasting.

^b Glutamate dehydrogenase testing is optional, but should be performed where sites have the capability to perform the test locally.

^c Collected at screening, pre-infusion on each dosing day, and end of treatment visit.

NB. Refer to [Appendix E](#) if alanine amino transferase or aspartate aminotransferase $\geq 3 \times$ ULN together with total bilirubin $\geq 2 \times$ ULN.

ULN, upper limit of normal range.

Results for LFTs must be available and reviewed before infusion of study treatment throughout Cycle 1 and review of results is recommended before each administration of study treatment from Cycle 2 and beyond. Values must have returned to the patient's baseline before infusion of AZD0466.

Clinical chemistry, including creatine phosphokinase, should be performed for Part A and B according to the schedule below.

- Screening
- Pre-infusion on each dosing day
- 24 hours (± 2 hours) after each dosing
- EoT visit

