12.6.2.9.4 Clinical Chemistry

Blood samples for determination of clinical chemistry will be collected as specified in [Table 25](#) and [Table 26](#). Unscheduled samples may be collected if deemed clinically warranted, and results of unscheduled assessment should be recorded in the eCRF.

If an unscheduled ECG is performed for patient assessment, an electrolyte panel (ie, calcium, magnesium potassium) must be done. If clinically indicated, a troponin assay should coincide with this evaluation. Cardiac troponin I is preferred when available, however if not, cardiac troponin T is acceptable. To allow comparison with baseline, sites are requested to maintain consistency with the troponin assay used. Isolated troponin elevations are not sufficient to trigger dosing changes and should be evaluated in the context of other cardiac findings.

The following clinical chemistry tests will be performed ([Table 28](#)).

Table 28 Clinical Chemistry

Albumin	Cholesterol ^a	Magnesium
Alkaline phosphatase	C-reactive protein	Phosphate
Alanine aminotransferase	Creatinine	Potassium
Amylase ^b	Gamma-glutamyl transferase	Sodium
Aspartate aminotransferase	Glucose ^a	Triglycerides ^a
Bicarbonate	Glutamate dehydrogenase ^b	Total protein
Bilirubin (total and direct)	Lactate dehydrogenase	Chloride
Blood urea nitrogen	Lipase ^c	Uric acid
Calcium		

^a Fasting cholesterol, triglyceride and glucose values are not required. However, if non-fasting values are abnormal, a repeat sample should be obtained when the patient is fasting.

^b Glutamate dehydrogenase testing is optional, but should be performed where sites have the capability to perform the test locally.

^c Collected at screening, pre-infusion on each dosing day, and end of treatment visit.

NB. Refer to [Appendix E](#) if alanine amino transferase or aspartate aminotransferase $\geq 3 \times$ ULN together with total bilirubin $\geq 2 \times$ ULN.

ULN, upper limit of normal range.

Results for LFTs must be available and reviewed before each infusion of study treatment throughout Cycle 1 and review of results is recommended before each infusion of study treatment from Cycle 2 and beyond. Values must have returned to the patient's baseline before infusion of AZD0466.

Clinical chemistry, including creatine phosphokinase, should be performed according to the schedule below (collection time begins from start of infusion).

- Screening
- Cycle 1 Period 1 and Period 3: Pre-infusion on each dosing day

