- Cycle 1 Period 1 and Period 3: 24 hours (± 2 hours) after each dosing
- At each cycle from Cycle 2 onwards: Pre-infusion on each dosing day
- At each cycle from Cycle 2 onwards: 24 hours (± 2 hours) after each dosing
- EoT visit

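### Module 2's benefit-risk text claims liver tests more frequent than other chemistry; the written schedule makes them more frequent only than amylase and lipase, with one post-dose test while voriconazole continues

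*Protocol*

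**What the plan says.** Section 12.1.6 of the protocol singles out liver function as the one overlap between voriconazole's common adverse reactions and the potential risks of AZD0466. In the next sentence it relies on "mandatory safety monitoring procedures, including intensive more frequent assessments of" "liver biochemistry than for other clinical chemistry parameters".

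The schedule is in Section 12.6.2.9.4. ALT, AST, ALP and bilirubin sit in Table 28 with the rest of the chemistry panel and share one list of times. In Cycle 1 the entries are "Cycle 1 Period 1 and Period 3: Pre-infusion on each dosing day" and "Cycle 1 Period 1 and Period 3: 24 hours" after each dose. From Cycle 2 the first entry is "At each cycle from Cycle 2 onwards: Pre-infusion on each dosing day", again with a 24-hour sample. The text gives no separate liver schedule.

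The same section sets a review rule. Liver results must be in hand and checked before every Cycle 1 infusion, but afterwards "review of results is recommended before each infusion of study treatment from Cycle 2 and beyond". The sentence that follows says "Values must have returned to the" patient's baseline before AZD0466 is given. Module 1 (Section 11.6.2.9.4) has the same pair of rules: "review of results is recommended before each administration of study treatment from Cycle 2 and beyond", followed by the same baseline requirement.

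**The concern.** A benefit-risk section is where ethics committees and investigators look for the safeguard that matches the named risk. Here they are told that the one shared toxicity is watched more closely than other chemistry. If the schedule does not do that, the statement should not stand.

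Hepatotoxicity is an adverse event of special interest (Section 8.3.12), safety is the module's primary objective, and Section 12.1.3 says the module will inform whether azole restrictions are kept or lifted. The combination itself is short: one AZD0466 infusion on Day 15, with voriconazole on Days 15 to 19. The liver data for that window therefore depend on what is scheduled in those five days.

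The review rule raises a second, smaller question. A requirement that values be back at baseline before infusion cannot be met reliably if looking at the result beforehand is only advised.

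**Working it through.** There is no figure in the plan to reproduce. The check is a count of scheduled draws per patient in Module 2 Cycle 1, excluding screening.

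**Inputs**
- AZD0466 infusions on Days 1, 4, 8 and 15, so 4 doses (Section 12.1.5).
- General panel: pre-infusion and 24 hours after each dose (Section 12.6.2.9.4).
- Amylase and lipase: pre-infusion only (Section 12.6.2.9.5).
- TLS checks: at least two in the 24 hours after each dose (Section 12.6.2.9.12), covering uric acid, potassium, phosphate, calcium and creatinine (Section 12.6.2.9.13).
- Voriconazole on Days 11 to 19. PK blood on Days 15 to 19, with the Day 17, 18 and 19 samples at 48, 72 and 96 hours (Section 12.6.3.1.1).

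**Counts**
1. Liver tests: 4 pre-infusion + 4 at 24 hours = 8 (Days 1, 2, 4, 5, 8, 9, 15, 16).
2. Other general-panel analytes: the same 8.
3. Amylase and lipase: 4.
4. Secondary comparison, TLS analytes: 4 pre-infusion + 4 × 2 post-dose = at least 12 if the 24-hour panel counts as one of the two checks. If it does not, 4 + 4 + 8 = at least 16.

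**Where liver tests stand.** Table 28 has 25 entries. Counting ALT, AST, ALP, bilirubin, GGT and glutamate dehydrogenase as liver tests (an assumption) leaves 19 others. Liver tests are drawn more often than 2 of these (amylase, lipase). On the panel schedule alone they match the other 17. If the extra TLS checks are counted, they match 12 and fall below 5.

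**Combination days (15 to 19).** Liver tests fall on Days 15 and 16, which is 2 of 5. Day 15 is pre-infusion, so 1 follows the combined dose. Days 17 to 19 have 0 of 3. The next scheduled liver test is pre-infusion on Cycle 2 Day 1. With a 21-day Cycle 1 that is nominally Day 22, six days after Day 16.

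**After the proposed fix.** Liver draws become 8 + 3 = 11. That exceeds the general panel's 8 but stays below the 12 for TLS analytes, so Section 12.1.6 needs exact wording in either case.

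**The case against.** Several points against the concern have force.

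- **The controlling table cannot be read.** Section 12.6.2.9 makes Tables 25 and 26 the source of timepoints. Table 25 has redacted rows and lost marks, so a liver row that is not visible cannot be excluded. A reader might take its empty chemistry cells after Day 16 as confirmation. They are not: its ECG row also shows no Period 3 marks, yet Table 27 schedules ECGs on Days 15 to 18. The finding rests on the text list only.
- **TLS monitoring is a separate schedule row.** Treating those extra draws as part of other clinical chemistry is an interpretation. Without them, liver tests are never drawn less often than another analyte. The comparison is therefore secondary.
- **Section 12.1.6 does not promise a test on each combination day.** It compares analytes. A reader might infer a broken promise about Days 17 to 19, but the text does not make one.
- **Liver-specific safeguards exist.** These are mandatory review in Cycle 1, the baseline rule, INR repeats after abnormal liver results (Section 12.6.2.9.7), the action rules in Table 8, Appendix E follow-up, and unscheduled chemistry. They respond to a result or rely on discretion, and none adds a scheduled liver draw.
- **Day 16 is a sensible time.** Section 2.1.2 expects rapid-onset, transient transaminase changes, and the Day 15 dose is reduced. No document gives a time course for the combination, so it is unknown whether 48 to 96 hours matters.
- **Cycle 2 Day 1 is less exposed than it may look.** In Table 22 the full target dose is 4 times the Day 15 dose in four rows, 3 times in the fifth (3600/1200) and 2.25 times in the last (5400/2400). A reader might infer a large step into untested exposure. However, the same patient already had the target dose on Day 8 with chemistry before and after it, voriconazole has stopped by then, and any higher dose must already have been declared tolerable in Module 1. Appendix E 3 also has the investigator review each new laboratory report without delay, though it does not tie that review to the infusion.

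These points narrow the concern. They do not supply the more frequent liver testing that Section 12.1.6 describes.

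**Conclusion.** The point holds in a limited form. In the visible text, liver biochemistry is on the general-panel schedule (8 draws against 8) and is drawn more often only than amylase and lipase (4). The stated safety property is therefore not delivered as described. Each patient has one scheduled liver test after the combined dose while voriconazole continues, and none on Days 17 to 19, although blood is taken on all three days.

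The sponsor already treats part of that window as a safety period: Table 27 has triplicate ECGs on Days 17 and 18, and the Amendment 1 history gives safety monitoring after the combined infusion as their reason.

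The documents do not show that liver injury would be missed or that any patient is harmed by the gap. The conclusion assumes that Table 25 contains no liver-only row hidden by damage or redaction.

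The pre-dose review inconsistency does not depend on Table 25. From Cycle 2 a mandatory baseline condition is paired with a review that is only advised, in both modules.

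**What to change.** 1. Add ALT, AST, ALP and total bilirubin to the blood already drawn for PK on Days 17, 18 and 19, as a separate Table 25 row and in Section 12.6.2.9.4. Cost: 3 panels × 10 to 14 patients = 30 to 42 panels, with no new visit. Assuming 3 to 5 mL per panel, that is 9 to 15 mL of blood per patient.
2. Reword Section 12.1.6 to state the actual schedule: liver biochemistry before and 24 hours after each AZD0466 infusion and, if item 1 is adopted, on Days 17, 18 and 19 of Period 3. If the draws are not added, delete the claim of greater frequency. This costs nothing.
3. Make pre-dose liver review required from Cycle 2 in Sections 12.6.2.9.4 and 11.6.2.9.4. No new sample is needed, because the pre-infusion panel is already scheduled on each dosing day. The small downside is that the infusion waits for the result, as it already does in Cycle 1.

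SAP Section 1 records that recruitment stopped on 16 June 2023 and that the study was then terminated, so item 1 can no longer change care in this trial. It remains a comment on the plan as written, and the study report should not repeat the Section 12.1.6 claim.

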12.2.1 Primary Objectives

See Section 3 of the core protocol.

12.2.2 Secondary Objectives

The secondary objective and endpoint for this module is listed in Table 23. See Section 3 of the core protocol for all other secondary objectives.

Table 23 Secondary Objective – Module 2

Objectives	Endpoints/Variables
Secondary	

To assess the drug-drug interaction potential between AZD0466 and the azole antifungal voriconazole.	
AUC and C_{max} of AZD4320 after administration of AZD0466 alone and in combination with voriconazole

12.2.3 Exploratory Objectives

See Section 3 of the core protocol for all other exploratory objectives.

12.3 STUDY POPULATION - MODULE 2

Core inclusion and exclusion criteria applicable to all patients enrolled in the study are listed in Section 5.1 and Section 5.2. There are no additional inclusion or exclusion criteria specific to Module 2.

Patients are eligible to be included in the dose escalation part of Module 2 if they meet all of the inclusion criteria in Section 5.1 and none of the exclusion criteria in Sections 5.2. Under no circumstances can there be exceptions to this rule.

Note: Each patient may only be enrolled in one module of this study. A patient who enrols in one module of this study is not eligible to participate in another module.

12.3.1 Inclusion Criteria

Refer to Section 5.1 of the core protocol for the common inclusion criteria applicable to Module 2.

12.3.2 Exclusion Criteria

Refer to the core protocol (Section 5.2). In addition, patients for whom treatment with voriconazole is contraindicated per the local prescribing information must not enter the study.

12.3.3 Lifestyle Considerations

Patients must comply with the restrictions described in the core study protocol (Section 5.3).

12.3.4 Concomitant Medications

Patients must comply with the restrictions described in the core protocol (Section 6.5)

12.3.5 Screen Failures

Refer to the core protocol (Section 5.4).

12.4 Study Treatment - Module 2

Information on the preparation, handling, storage, accountability of study treatment, measures to minimise bias, and study treatment compliance and accountability is either provided in Table 24 and/or referenced in the core protocol (Section 6).

12.4.1 Study Treatment(s) – AZD0466 and Voriconazole

AZD0466 and voriconazole are described in Table 24.

Table 24 **Study Treatment for Module 2**

Study Treatment	AZD0466	Voriconazole
Dose Formulation	‘AZD0466 powder for concentrate for solution for infusion’ supplied with ‘Solvent for AZD0466 powder for concentrate for solution for infusion’.	Film-coated tablet
Unit Dose Strength(s)	‘AZD0466 powder for concentrate for solution for infusion’: 500 mg per vial ^a ‘Solvent for AZD0466 powder for concentrate for solution for infusion’: 20 mL per vial ^a	50 mg, 100 mg, and 200 mg
Dose Level	Dose level of AZD0466 that has been declared tolerable in Module 1 Part A	See Figure 4
Route of Administration	Intravenous	Oral
Dosage preparation and administration	Refer to Handling Instructions	Product should be administered in accordance with the prescribing information.
Provider	AstraZeneca R&D	Provided locally by the study site, subsidiary, or designee ^b
Packaging and Labelling	AZD0466 powder for concentrate for solution for infusion will be provided in 500 mg vials. Each vial will be labelled as per country requirement. Solvent for AZD0466 powder for concentrate for solution for infusion will be provided in 20 mL vials. Each vial will be labelled as per country requirement.	Voriconazole will be provided as a commercial film-coated tablet presentation in a commercial pack.

^a AZD0466 powder for concentrate for solution for infusion 500 mg/vial is intended to be reconstituted with 20 mL custom solvent to produce AZD0466 concentrate for solution for infusion, 25 mg/mL. If required AZD0466 concentrate for solution for infusion may be further diluted with custom solvent to produce AZD0466 solution for infusion for clinical dosing. Multiple vials of drug product and custom solvent may be used to achieve the required doses.

^b Under certain circumstances when local sourcing is not feasible treatment may be supplied centrally through AstraZeneca. In the event of central supply voriconazole will be labelled as per country requirement for clinical trial use.

During ramp-up and while patients are considered at risk of TLS, patients must commence oral allopurinol and be encouraged to drink 1.5 to 2 L of fluid at least 24 hours prior to AZD0466 infusion ([Appendix F](#)).

Patients will receive study treatment in Cycle 1 of Module 2 as follows:

- Period 1: AZD0466 ramp-up
Patients will be admitted to hospital and receive a starting ramp-up dose of AZD0466 on Day 1, with subsequent intra-patient ramp-up to an intermediate dose on Day 4, and to the target dose on Day 8. The Day 1 and Day 4 ramp-up doses will be equivalent to those used for that target dose in Module 1.
- Period 2: Voriconazole administration
Patients will receive voriconazole 400 mg twice daily (BID) on Day 11 and voriconazole 200 mg BID on Day 12-14.
- Period 3: AZD0466 in combination with voriconazole
Patients will be admitted to hospital and receive AZD0466 on Day 15 at a reduced dose (ie, dose equivalent to the Day 1 dose) and voriconazole 200 mg BID will continue from Day 15 until Day 19. Voriconazole administration on Day 19 will not continue beyond the time of last PK sample collection.

Voriconazole tablets should be taken at least one hour before or one hour after a meal, on each of the voriconazole dosing days.

Patients who continue to receive AZD0466 in Cycle 2 may receive AZD0466 at a higher target dose if a new higher dose level was declared tolerable in the dose escalation part of Module 1. Cycle 2 and subsequent cycles are 28 days in duration in which AZD0466 is administered once weekly on Days 1, 8, 15, and 22 of each cycle. All patients will be treated until progressive disease, unacceptable toxicity or withdrawal of consent.

12.4.2 Preparation, Handling, Storage, and Accountability of Study Treatment

Refer to the core protocol (Section 6.2) for AZD0466. Voriconazole should be stored according to the storage conditions indicated on the product label.

12.4.3 Measures to Minimise Bias

Refer to the core protocol (Section 6.3).

12.4.4 Study Treatment Compliance

Refer to the core protocol (Section 6.4).

12.4.5 Intervention After the End of the Study

Refer to the core protocol (Section 6.8).

12.5 STUDY PLAN AND TIMING OF PROCEDURES – MODULE 2

12.5.1 Schedule of Activities

The SoA for Periods 1, 2, and 3 (Cycle 1) and for subsequent cycles are shown in [Table 25](#) and [Table 26](#).

Table 25 Module 2 - Schedule of Activities for Screening and Cycle 1

Procedure	Screening	Cycle 1 (21 days)										Details in CSP Section or Appendix					
		Period 1 AZD0466 ^a					Period 2 Voriconazole			Period 3 AZD0466 + Voriconazole							
Day	-28 to -1	1	2	3	4	5	6	7	8	9	10	11-14	15	16	17	18	19
Informed consent	X																Appendix A.3
Inclusion and exclusion criteria																	5.1; 5.2; 12.3.1; 12.3.2
Demography	X																8
Medical history	X																8
Physical examination	X	X	X	X	X	X	X	X	X	X	X	X	X	X	X	X	12.6.2.1
Height	X																12.6.2.3
Weight	X	X										X					12.6.2.3
Vital signs ^b	X	X*	X	X	X*							X*	X	X	X	X	12.6.2.5
Chest X-ray ^c	X																12.6.2.4
ECOG performance status	X	X															12.6.2.7
Concomitant medication	X	X	X	X	X	X	X	X	X	X	X	X	X	X	X	X	12.3.4
Adverse events (AE)	X	X	X	X	X	X	X	X	X	X	X	X	X	X	X	X	8.3
CCI	■																■
Safety ECG (triplicate)	X	X*	X	X*	X												12.6.2.6
Cardiac MUGA/MRI/ECHO ^d	X																12.6.2.7
Laboratory Tests																	
COVID-19 test		X															12.6.2.9.1

Table 25 Module 2 - Schedule of Activities for Screening and Cycle 1

Procedure	Screening	Cycle 1 (21 days)										Details in CSP Section or Appendix					
		Period 1 AZD0466 ^a					Period 2 Voriconazole			Period 3 AZD0466 + Voriconazole							
Day	-28 to -1	1	2	3	4	5	6	7	8	9	10	11-14	15	16	17	18	19
Hepatitis B and C, HIV and CMV	X																
Pregnancy test (WOCBP only)	X	X															12.6.2.9.3
CBC with differential	X	X*	X									X*	X				12.6.2.9.6
CCI [REDACTED] ^e																	
Clinical chemistry	X	X	X									X	X				12.6.2.9.4
TLS monitoring ^f												X*	X*				12.6.2.9.12 and 12.6.2.9.13
CPK	X	X	X									X	X				12.6.2.9.4
Coagulation indices	X	X										X					12.6.2.9.7
Cardiac troponin I ^g	X																12.6.2.9.8
BNP (or NTproBNP)	X																12.6.2.9.8
Cortisol, ACTH, TSH	X																12.6.2.9.9
Amylase and lipase	X	X										X					12.6.2.9.5
Serum immunoglobulins	X											X					12.6.2.9.10
Urinalysis	X	X										X					12.6.2.9.11
CCI [REDACTED]																	
Overnight inpatient stay ^h		X										X					12.6.2.9.12
Administer AZD0466		X										X					6.1 and 12.1.5

Table 25 **Module 2 - Schedule of Activities for Screening and Cycle 1**

- a Any visits (eg, Day 6 and Day 7) that do not require attendance at the site for blood draw or physical examination can be conducted by telephone, at the Investigator's discretion.
- b On PK sampling days, blood pressure readings to be taken at each PK sample timepoint. All blood pressure readings can be taken \pm 10 minutes from the designated PK sample collection.
- c Chest X-rays may also be performed at other timepoints during the study at the Investigator's discretion, when clinically indicated.
- d Cardiac MUGA/MRI/ECHO to assess left ventricular ejection fraction will be conducted. Ensure the same modality is used for each patient. Unscheduled assessment if deemed clinically warranted.
- e **CCI**
- f At least twice in the first 24 hours after each administration of AZD0466, and as clinically indicated thereafter as per institutional protocol.
- g Cardiac troponin to be collected at screening (baseline) and at other timepoints in the study, as clinically indicated. Cardiac troponin I is preferred if available, if not, cardiac troponin T is acceptable. To allow comparison with baseline, sites are requested to maintain consistency with the troponin assay used.
- h Additional inpatient admission days at Investigator discretion.
- i To be collected at screening between Day -28 and -1. When it is not possible to obtain a new bone marrow biopsy, a historic bone marrow biopsy sample may be used if collected within 28 days of first dose of AZD0466, but a historic bone marrow biopsy sample collected within 14 days of the first dose is preferred.

*Indicates more than one assessment is to be performed at the visit.
 ACTH, adrenocorticotrophic hormone; AE, Adverse event; BNP, brain natriuretic peptide; CBC, complete blood count; CMV, cytomegalovirus; COVID-19, coronavirus disease 2019; CPK, creatine phosphokinase; ECHO, echocardiogram; ECOG, Eastern Cooperative Oncology Group; HIV, human immunodeficiency virus; MRI, magnetic resonance imaging; MUGA, multigated acquisition; **CCI**, thyroid stimulating hormone; TLS, tumour lysis syndrome; WOCBP, women of childbearing potential.

Table 26 Module 2 - Schedule of Activities for Cycle 2 and beyond

Procedure	Cycle 2				Cycle 3 onwards (28-day cycles)				EoT	Post treatment follow-up ^a	Survival follow-up	Follow-up	Details in CSP Section or Appendix	
	Day	1	2	8/15/22	9/16/23	1	2	8	9/16/23	15/22				
Visit window											± 2 days	± 7 days	± 14 days	
Physical examination	X	X	X	X	X	X	X	X	X	X				12.6.2.1
Weight	X		D15		X					D15	X			12.6.2.3

Table 26 Module 2 - Schedule of Activities for Cycle 2 and beyond

Procedure	Cycle 2				Cycle 3 onwards (28-day cycles)				EoT	Post treatment follow-up ^a	Survival follow-up	Follow-up	Details in CSP Section or Appendix		
	Day	1	2	8/15/22	9/16/23	1	2	8	9/16/23	15/22	28 days after last dose	Every 1 month after last dose			
Visit window						±2 days				±7 days		±7 days		±14 days	
Vital signs ^b	X*	X	X*		D9	X*		X*		Every disease assessment in (D23-D28)	X*	X			12.6.2.5
ECOG performance status	X					X					X				12.6.2.8
Concomitant medication	X	X	X			X		X	X	X	X	X			12.3.4
Adverse events	X	X	X			X		X	X	X	X	X			8.3
Safety ECG (Triplicate)	X*	X	D8*		D9			X*	(even cycles only from C4)			X			12.6.2.6
Cardiac MUGA/MRI/ECHO ^c			D8						Every 3 Cycles from C5			X			12.6.2.7
Laboratory Tests															
COVID-19 test	X					X					X				12.6.2.9.1
Pregnancy test (WOBCP only)	X					X					X				12.6.2.9.3

Table 26 Module 2 - Schedule of Activities for Cycle 2 and beyond

Procedure	Cycle 2				Cycle 3 onwards (28-day cycles)				EoT	Post treatment follow-up ^a	Survival follow-up	Details in CSP Section or Appendix	
	Day	1	2	8/15/22	9/16/23	1	2	8	9/16/23	15/22	28 days after last dose	Every 1 month after last dose	
Visit window						±2 days				±2 days		±7 days	
CBC with differential	X	X	X	X ^e	X	X	X	X	X ^e	X	X	X	12.6.2.9.6
CCl ₄ ^d													
Clinical chemistry	X	X	X	X	X	X	X	X	X	X	X	X	12.6.2.9.4
TLS monitoring ^f	X*	X*	D8*	D9*									12.6.2.9.12 and 12.6.2.9.13
CPK	X	X	X	X	X	X	X	X	X	X	X	X	12.6.2.9.4
Coagulation indices	X	X	X		X		X		X	X	X	X	12.6.2.9.7
Cortisol, ACTH and TSH											X		12.6.2.9.9
Amylase and lipase	X	X		X		X		X		X	X	X	12.6.2.9.5
Serum immunoglobulins											X		12.6.2.9.10
Urinalysis	X	X		X		X		X		X	X		12.6.2.9.11
Overnight inpatient stay	X		D8										12.6.2.9.12
Administer AZD0466	X		X		X		X		X		X		6.1

Table 26 Module 2 - Schedule of Activities for Cycle 2 and beyond

Procedure	Cycle 2						Cycle 3 onwards (28-day cycles)			EoT	Post treatment follow-up ^a	Survival follow-up	Follow-up	Details in CSP Section or Appendix
	Day	1	2	8/15/22	9/16/23	1	2	8	9/16/23	15/22				
Visit window											±2 days	±7 days	±14 days	
Pharmacokinetic assessments														
Blood sample for plasma PK	X*					X*								12.6.3.1.1
Pharmacodynamic assessments														
CC1														
Blood for pharmacodynamic CC1														12.6.3.2.2
Blood for peripheral blood smears	X	X										X		12.6.1

Table 26 Module 2 - Schedule of Activities for Cycle 2 and beyond

Patients will be followed during the off-treatment period until all treatment related toxicity resolves, or for at least 28 days post-study drug discontinuation or until new therapy. This can be done via telephone contact at the Investigator's discretion.

- b On PK sampling days, blood pressure readings to be taken at each PK sample timepoint. All blood pressure readings can be taken \pm 10 minutes from the designated PK sample collection.
- c Cardiac MUGA/MRI/ECHO to assess left ventricular ejection fraction will be conducted. Ensure the same modality is used for each patient. Unscheduled assessment if deemed clinically warranted.
- d Part of collection to be used for peripheral blood smears.
- e If disease assessment is not on Day 23, an additional CBC sample is required.
- f At least twice in the first 24 hours after each administration of AZD0466, and as clinically indicated thereafter as per institutional protocol.
- g To be taken at Cycle 2 Day 16 or 17 and Cycle 3 Day 23-28 or as clinically indicated. If bone marrow is performed on day of infusion must be at least 6 hours post-infusion.

12.6 STUDY ASSESSMENTS AND PROCEDURES - MODULE 2

Study procedures and their timings for this module are summarised in the SoA (Section 12.5.1). Patient demographic characteristics, medical history and disease characteristics will be recorded as described in Section 8, Enrolment and Screening.

